9.1 Introduction

Effective vaccinations induce potent protective humoral and cellular immunity and promote development of robust T and B cell memory, together preventing infection and accelerating viral clearance following pathogen exposure. Current concepts are that vaccination results in activation of both T cells and B cells. Vaccine antigen-activated B cells can differentiate into low affinity IgG- or IgM-secreting plasma cells (PCs). Alternatively, vaccine antigen-activated B cells can interact with antigen-activated CD40+ CD4+ (Th1) helper T cells to undergo an isotype switch and enter germinal center (GC) reactions wherein they undergo affinity maturation. Positive selection of the highest affinity B cells in the GC requires cognate interactions with antigen specific IL-21-producing follicular helper CD4+ T cells (Tfh). The positively selected high affinity B cells then can differentiate into long lived antibody-secreting PCs, can become memory B cells (Bmem), or can reenter the GC to undergo further affinity maturation. Crucial features of the antibody repertoire relevant to pathogen clearance include antibody specificity, affinity, titer, isotype class, and glycosylation patterns, among others. Antigen-reactive CD4+ and CD8+ T cells that expand and differentiate following vaccination are also crucial mediators of pathogen clearance independent of their functions as helper cells for effective humoral immune responses. Important characteristics of these induced T cell responses include epitope specificity, cytokine secretion patterns, and cytotoxic function, among others. Effective anti-pathogen immunity also involves activation of innate immune cells, including dendritic cells, macrophages, and natural killer cells that can interact with and enhance the adaptive immune responses and have been recently shown to exhibit cellular and molecular features consistent with memory.

As noted in the background section, emerging evidence indicates that the majority of transplant recipients taking immunosuppressant medications do not produce effective antibody responses to SARS-CoV-2 spike protein mRNA vaccinations. Whether these patients develop and maintain protective T cell responses after the same vaccines is not known. A detailed kinetic analysis of innate and adaptive immunity following SARS-CoV-2 mRNA vaccination, particularly comparing responders to non-responders, is thus essential in order to interpret the clinical trial outcome and to guide design of follow up studies aimed at overcoming identified defects. Moreover, if it were possible to identify an early post vaccine molecular signature that correlates with vaccine success vs failure, such a biomarker could be used to guide subsequent strategies aimed at enhancing induction protective immunity in each transplant patient.

Thus, the overall goals of the proposed mechanistic studies are to a) characterize the vaccine-induced innate and adaptive immune responses in each study subject, b) compare the induced immune responses among participants in the various treatment arms, c) define the durability of the responses over 1-year post vaccination, d) provide insight into immune mechanisms that prevent formation and/or durability of the induced responses within each and among treatment arms, d) identify molecular markers of successful vaccination.

To this end we will serially collect serum, plasma, PBMC, and oral fluid samples over the entire study period. Using these samples we will a) quantify spike protein production in serum, b) provide a detailed kinetic characterization of the vaccine induced antibody repertoire (specificity, isotype, titer, neutralization capacity), c) perform a kinetic phenotypic and functional analysis of antigen specific Bmem (frequency, antigen specificity, surface markers, metabolomics, gene expression patterns, single cell sequencing) and

PC, d) perform a kinetic, analysis of antigen specific CD4+ and CD8+ T cells (frequency, epitope specificity, surface markers, metabolomics, gene expression patterns single cell sequencing), e) assess phenotypic, functional and gene expression patterns of innate immune DC, monocyte/macrophage and NK cell subsets in peripheral blood, and f) perform genomic profiling of peripheral blood cells that will provide a biomarker for an effective response.

9.2 Objective 1: To quantify spike protein production in serum or plasma after vaccination.

Transient expression of a modified spike protein using mRNA vaccines (Moderna and Pfizer-BioNTech) has been crucial in the global effort to control the SARS-CoV-2 pandemic. This platform offers the flexibility for rapid modification to control variants. Given the requirement for effective protein expression of immunogen, the extremely poor responses of transplant recipients, particularly those on mycophenolate mofetil raises the question whether the anti-metabolite properties of MMF may impair the transient expression of spike protein thereby contributing to the impaired vaccine response of transplant patients. Using a recently developed ultrasensitive molecular assay to detect spike protein in plasma we will assess expression in a subset of antibody negative study participants at baseline (pre-vaccine) and 3 days post-vaccination.

9.3 Objective 2: To provide a detailed kinetic characterization of the vaccine-induced antibody repertoire (specificity, isotype, titer, neutralization capacity).

While relative contributions of vaccine induced humoral and T cell immunity in the protection from severe SARS-CoV-2 disease are not fully understood, the development of a critical level of SARS-CoV-2 Ab are emerging as a correlate of protection. A detailed understanding of the profile of Ab responses in transplant recipients after vaccination is crucial step toward understanding what population benefits from an additional dose of vaccine. This objective will provide a deeper mechanistic characterization of to support hypothesis generating observations to understand the mechanisms underlying vaccine failure and to identify candidate humoral biomarkers to predict vaccine response. This includes surrogate and live virus neutralization titers including versus novel variants of concern.

9.4 Objective 3: To perform a kinetic phenotypic and functional analysis of antigen-specific Bmem (frequency, antigen specificity, surface markers, metabolomics, gene expression patterns, single cell sequencing) and PC.

To identify and characterize SARS-CoV-2 memory B cells we will use fluorescently labeled multimerized probes for targets of the vaccine (spike receptor-binding and ectodomain) and as well as non-vaccine expressed SARS-CoV-2 antigens (e.g. Nucleocapsid). The magnitude and differentiation of anti-specific IgM+ and IgG+ memory B cells will be assessed at each time point. We will use flow cytometry, CyTOF, single B cell multi-omics (cell surface CITE-seq profiling using tagged antibody and multimerized probes for vaccine targets), transcriptomics, and B cell receptor VDJ repertoire analysis to characterize antigen specific B cells. We will perform in vitro ELISPOT assays to determine frequencies of antigen specific PCs in peripheral blood.

9.5 Objective 4: To perform a kinetic, analysis of antigen-specific CD4+ and CD8+ T cells (frequency, epitope specificity, surface markers, metabolomics, gene expression patterns single cell sequencing).

While the requirements for sustained protection against SARS-CoV-2 are not yet known, effective control of viral pathogens often depends on the development of both humoral and cellular immunity.

We will assess the strength, breadth and character of the anti-spike T cell response in study participants using flow-cytometry based, ELISPOT, and single cell-multi-omics assays. Antigen-specific cells will be interrogated using a rapidly evolving set of peptide and MHC multimer reagents using flow-cytometry, CyTOF, and or ELISPOT readouts. For flow-based analysis we will utilize 1) antigen specific functional assays (activation-induced marker (AIM), intracellular cytokine secretion assays and novel T cell metabolic profiling assays and, 2) phenotypic characterization of spike-specific T cells MHC-peptide multimer staining. We will use single T cell multi-omics (cell surface CITE-seq profiling using tagged antibody and tetramers, transcriptomics, and T cell receptor VDJ repertoire analysis).

Exploratory immune profiling assessments will include:

9.6 Objective 5: To assess phenotypic, functional and gene expression patterns of innate immune DC, monocyte/macrophage and NK cell subsets in peripheral blood.

We will characterize the kinetics of peripheral blood immune landscape of mononuclear leukocyte lineage and phenotypic markers to broadly assess the immunological cellular profile of transplant recipients before and after vaccination, focusing on the absolute and relative frequency of T, B, NK and APC subsets.

We will characterize these cell types in peripheral blood using flow cytometry and or CyTOF assays. We will test function using in vitro assays that include in vitro stimulation of DC subsets with TLR ligands (cytokine and surface marker readouts as measures of activation), in vitro stimulation of macrophages with LPS (cytokine readouts as a measure of trained immunity, which would then be followed up with epigenetic analyses), in vitro functional analyses of NK cells.

9.7 Objective 6: Exploration of molecular biomarkers of early responders to vaccination

We will collect serial blood samples for RNA profiling (RNAseq) and/or proteomics in addition to characterization of cytokine signaling early after vaccine intervention.

10. Biospecimen Storage

Biological specimens obtained under this protocol may be used in future assays to reevaluate biological responses as additional research tests are developed over time. These may include, but are not limited to, tests examining aspects of host immunology, cell biology, or human genetics as it relates to any of these aspects. Appropriate informed consent will be obtained for both the collection and storage of samples. The specimens from these evaluations will be labeled with a coded ID and may be stored beyond the funding period.

11. Criteria for Participant and Study Completion and Premature Study Termination

11.1 Participant Completion

All participants will be followed for 12 months following the COVID-19 vaccine administration.

11.2 Participant Stopping Rules and Withdrawal Criteria

Participants may be prematurely terminated from the study for the following reasons:

1. The participant elects to withdraw consent from all future study activities, including follow-up.
2. The participant is “lost to follow-up” (i.e., no further follow-up is possible because attempts to reestablish contact with the participant have failed).
3. The participant dies.
4. The Investigator no longer believes participation is in the best interest of the participant.

11.3 Participant Replacement

Participants who withdraw or are withdrawn will not be replaced.

11.4 Follow-up after Early Study Withdrawal

If a participant is withdrawn from the study for any reason, the participant may be asked to complete a final visit and/or final assessments.

11.5 Study Pausing Rules

If the following occur, relevant study interventions will be temporarily halted pending a DSMB review and recommendation as to whether the study may proceed.

1. Any Grade 4 or 5 event that is definitely or possibly attributed to the study dose of vaccine or to immunosuppression reduction.
2. Any probable or confirmed case of either acute myocarditis or acute pericarditis that occurs within 6 weeks of the study vaccine.
3. **Excess incidence of acute rejection (clinically treated or biopsy-proven):** Based on registry data, approximately 5-6 rejection events would be expected over the course of the study, independent of any effect of the study interventions. A pausing rule has been constructed such that the study would be paused if there is a >50% chance that the observed event rate exceeds three times the expected rate. The pausing rule will be applied to the study by group: (1) COVID-19 vaccine dose alone (2) MMF withdrawal (3) CNI reduction. Event rates triggering a pause are shown below:

Number of participants	Number of events required to trigger a pause	Event rate required to trigger a pause
10	3	30%
20	3	15%
30	3	10%
40	4	10%
50	4	8%
75	4	5%
100	5	5%
150	6	4.0%

200	7	3.5%
250	8	3.2%
300	9	3.0%
350	10	2.9%
400	11	2.8%

4. **Excess incidence of graft loss:** Based on registry data, it is expected that there will be approximately 6-7 graft losses over the course of the study, independent of any effect of the study interventions. A pausing rule has been constructed such that the study would be paused if there is a >50% chance that the observed event rate exceeds three times the expected rate. The pausing rule will be applied to the study by group: (1) COVID-19 vaccine dose alone (2) MMF withdrawal (3) CNI reduction. Event rates triggering a pause are shown below:

Number of participants	Number of events required to trigger a pause	Event rate required to trigger a pause
10	3	30%
20	3	15%
30	3	10%
40	4	10%
50	4	8%
75	4	5%
100	5	5%
150	6	4.0%
200	7	3.5%
250	8	3.2%
300	9	3.0%
350	10	2.9%
400	11	2.8%

5. **Excess Mortality:** Based on registry data, it is expected that there will be approximately 5 deaths over the course of the study, independent of any effect of the study interventions. A pausing rule has been constructed such that the study would be paused if there is a >50% chance that the observed event rate exceeds three times the expected rate AND is determined to be possibly, probably or definitely related to a study intervention. The pausing rule will be applied to the study overall and by group: (1) COVID-19 vaccine dose alone (2) MMF withdrawal (3) CNI reduction. Event rates triggering a pause are shown below:

Number of participants	Number of events required to trigger a pause	Event rate required to trigger a pause
10	3	30%
20	3	15%
30	3	10%
40	4	10%
50	4	8%
75	4	5%
100	5	5%
150	5	3.3%
200	6	3.0%
250	7	2.8%
300	8	2.7%
350	9	2.6%
400	10	2.5%

12. Safety Monitoring and Reporting

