Primary Endpoint(s)	The primary endpoint is the -fold increase in antibody titer (using the Roche Elecsys® anti-SARS-CoV-2 S assay) from before receiving the study dose of vaccine to 30 days after the study dose.
Safety, Secondary, and Exploratory Endpoint(s)	
Secondary Safety Endpoints:
 
 Local and systemic vaccine reactogenicity and/or allergy Serious adverse events occurring during the 30 days following the additional dose of vaccine Treated acute cell-mediated and/or antibody-mediated allograft rejection (clinical or biopsy-proven) within 60 days following the additional dose of vaccine Development of de novo donor-specific anti-HLA antibody within 90 days of the vaccine Graft loss within 60 days of the vaccine Death within 60 days of the vaccine 
Secondary Efficacy Endpoints:
 
 Duration of anti-SARS-CoV-2 S antibody titers and neutralizing capacity in the year following the additional dose of vaccine

	
SARS-CoV-2 PCR positivity
 
Symptomatic COVID-19
 
COVID-19 requiring hospitalization
 
Log SARS-CoV-2 antibody titer at 30 days post-vaccine
 
Longitudinal changes in log SARS-CoV-2 antibody titer during the study
 
Exploratory Mechanistic Endpoints:
 
Anti-S1 and anti-RBD serology
 
Detection of SARS-CoV-2 spike protein in blood after the additional dose of vaccine
 
Additional serological panels and correlates of neutralizing antibody
 
SARS-CoV-2 virology, diagnostics, and sequencing, including novel variants of concern
 
Oral fluid anti-N and anti-S immunoglobulin levels (IgA (total and secretory), IgM, IgG)
 
Antigen-specific B cell response
 
Antigen-specific T cell response
 
Evidence of immune activation, transcriptomics and cytokine signaling
 
Durability of de novo donor-specific anti-HLA antibody

Accrual Objective	400 transplant kidney and liver transplant recipients with negative or low (≤ 2500 U/mL) antibody titers using the Roche Elecsys® anti-SARS-CoV-2 S assay after an authorized or licensed mRNA based anti-COVID-19 vaccination regimen.
Study Duration	
Accrual: 4 months
 
Screening, Vaccination and Follow-up: 13 months
 
Total Duration: 17 months

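### The rejection and graft-loss pausing tables ignore follow-up time, so during accrual their triggers generally sit above the stated three-fold excess, by an amount that depends on assumptions the plan leaves unstated

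*Combined protocol and SAP*

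**What the plan says.** Section 11.5 gives background counts for three events. For rejection, "approximately 5-6 rejection events would be expected over the course of the study". For graft loss, "it is expected that there will be approximately 6-7 graft losses over the course of the study". For mortality, "it is expected that there will be approximately 5 deaths over the course of the study". The criterion common to all three is that "the study would be paused if there is a >50% chance that the observed event rate exceeds three times the expected rate".

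Each table lists a number of participants, the number of events that triggers a pause, and a column headed "Event rate required to trigger a pause", which is events divided by participants. Rejection and graft loss share the same entries, including 5 of 100, 6 of 150, 7 of 200 and 11 of 400. For these two events, "The pausing rule will be applied to the study by group: (1) COVID-19 vaccine dose alone (2) MMF withdrawal (3) CNI reduction".

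Section 11.1 says "All participants will be followed for 12 months following the COVID-19 vaccine administration". The synopsis gives "Accrual: 4 months" and describes the tabulated rates as triggering a pause in enrollment. Section 13.7 plans 200 participants per arm. The documents do not say which time window the expected counts cover. They also do not say whether participants means enrolled, vaccinated or fully followed.

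**The concern.** The two sides of the comparison are on different time bases. The expected count accumulates over whatever window the sponsor had in mind. The observed count accumulates only over the time each person has been followed, yet a participant vaccinated yesterday adds a full unit to the denominator. While enrollment is open, many participants have short follow-up, so the observed rate is understated and the trigger is harder to reach than the criterion implies.

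A pause mainly protects people who have not yet started the reduction, so its behaviour during accrual is what matters. Reading participants as those with complete follow-up does not help under the stated plan. With 12 months of follow-up and a 4-month accrual, the first evaluable participant arrives about 8 months after enrollment closes.

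**Working it through.** **Inputs.** Expected rejections: 5.5 (midpoint of 5-6, section 11.5), taken as the count for all 400 participants, so p0 = 5.5/400 = 1.375%. Triggers: 5 at n = 100 and 7 at n = 200. Stated accrual: 4 months. Assumptions of this review: uniform accrual; a window W of 12 months (inferred from section 11.1) or 60 days, taken as 2 months (the window of the secondary safety endpoints in section 3.3.1); and accrual of 12 or 24 months as sensitivity cases.

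**Step 1: the plan's own table.** Three times p0 is 4.125%. A plain ratio above that needs more than 8.25 events in 200, so 9, and more than 16.5 in 400, so 17. The table has 7 and 11. With 5-6 expected events, the flat-prior, Jeffreys, simple-ratio and median-bound versions of the criterion give 7-10 at 200 and 15-19 at 400. The rejection table is reproduced exactly by a Beta(1, 1/p0 - 1) prior, but only with 2.6-2.9 expected events per 400, about half the stated count. So the table does not follow from its stated input even with complete follow-up. That is a separate inconsistency, but it affects the baseline:

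- n = 100, complete follow-up: 5 / (100 x 0.01375) = 5/1.375 = 3.6 times expected.
- n = 200, complete follow-up: 7 / (200 x 0.01375) = 7/2.75 = 2.5 times expected.

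**Step 2: observed share of the window.** When n of a group of G have entered over A months, elapsed time is t = A x n/G. The mean observed share is f = t/(2W) if t ≤ W, and f = 1 - W/(2t) if t > W. Expected events so far are n x p0 x f. The trigger as a multiple of expectation is the Step 1 figure divided by f.

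Group of 200, rejection:

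| Window W | Accrual A | f at n=100 | Multiple at n=100 | f at n=200 | Multiple at n=200 |
|---|---|---|---|---|---|
| 12 months | 4 months | 0.083 | 44 | 0.167 | 15 |
| 12 months | 12 months | 0.25 | 15 | 0.50 | 5.1 |
| 12 months | 24 months | 0.50 | 7.3 | 0.75 | 3.4 |
| 60 days | 4 months | 0.50 | 7.3 | 0.75 | 3.4 |
| 60 days | 12 months | 0.83 | 4.4 | 0.92 | 2.8 |
| 60 days | 24 months | 0.92 | 4.0 | 0.96 | 2.7 |

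Example, first row: 100 x 0.01375 x 0.083 = 0.115 expected events, and 5/0.115 = 44. At n = 200, 0.458 are expected and 7/0.458 = 15. For graft loss (6.5 expected per 400) the corresponding figure at n = 200 is 7/0.542 = 13.

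**Step 3: the reduction groups.** MMF withdrawal and CNI reduction share about 200 participants, and the split is not stated. For a group of 100, on a 12-month window, the trigger of 5 at n = 100 is about 22, 7 and 4.8 times expected with 4-, 12- and 24-month accrual, against 3.6 with complete follow-up.

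**Step 4: chance of a pause by the end of accrual** (rejection, group of 200, 12-month expected counts). At a constant three-fold hazard and 4-month accrual, the mean count is 3 x 0.458 = 1.375, and the Poisson probability of 7 or more is 0.06%. With a full year for everyone the mean is 8.25 and the probability is 72%.

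Simulation applied the table at each event. The person-time comparator pauses when there are at least 3 events and the median of Gamma(x + 0.5), divided by the events expected in the accrued time, exceeds 3.

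| True excess | Accrual | Table | Person-time |
|---|---|---|---|
| five-fold, constant over 12 months | 4 months | 1% | 41% |
| five-fold, constant over 12 months | 12 months | 51% | 92% |
| five-fold, constant over 12 months | 24 months | 89% | 97% |
| three-fold, excess in first 2 months | 4 months | 18% | 83% |
| three-fold, excess in first 2 months | 24 months | 63% | 87% |

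If a five-fold 12-month total falls with its excess in the first 2 months, the table pauses about 77% of the time with 4-month accrual. At the expected rate, the table pauses in under 1% of trials and the person-time version in about 1-12%.

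**The case against.** The strongest reply has four parts.

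- **Window.** The 12-month window is inferred. The plan's safety endpoints for rejection, graft loss and death use 60 days. If the registry counts do too, the trigger at n = 200 is close to three-fold. This stands, and it is why a range is given.
- **Accrual.** The 4-month figure sits in a protocol that section 6 shows moving through monovalent, bivalent and 2023-2024 vaccines, so enrollment evidently ran longer. This also stands; slower accrual shrinks the gap.
- **Timing of the hazard.** The reduction is brief, so any excess may come early. A reader might take the 1% detection figure as a property of the rule. It is not: it needs a constant hazard over 12 months and 4-month accrual, and it rises to about 77% if the excess is early. The gap to person-time nevertheless persists at three-fold.
- **Other safeguards.** One possibly related Grade 4 or 5 event already pauses the study (section 11.5, rule 1). There are also Class II dnDSA looks in kidney recipients (13.5.2), monthly medical monitor reports (12.7.1) and discretionary DSMB reviews (12.7.2.1). These reduce the consequences, but none is a numerical check on rejection or graft loss of lower grade or not attributed to the study. The planned DSMB review comes one month after all participants are vaccinated.

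Below about 75 participants, part of the high multiple is simply small numbers: 4 of 50 is 5.8 times expected even with complete follow-up.

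**Conclusion.** The tables have no exposure basis. Followed as written, the rejection and graft-loss rules do not deliver their stated criterion during accrual. In most scenarios examined the trigger is above three-fold. For rejection in a group of 200, it runs from 44 and 15 times expected at n = 100 and 200 (12-month window, 4-month accrual) to 4.0 and 2.7 times (60-day window, 24-month accrual).

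A reader might infer that the rules always pause at many times the intended excess. The documents do not support that: the window is unstated, accrual may exceed 4 months, and with complete follow-up the entry at 200 is 2.5 times expected, below three-fold. Nor does the point carry much weight for mortality. That rule counts only related deaths, and one possibly related Grade 5 event already triggers a pause. The results assume uniform accrual and 5.5 rejections per 400; using 5 or 6 moves the n = 200 figure with 4-month accrual only between 17 and 14. This should be fixed, but the case does not support calling it critical.

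**What to change.** In section 11.5 and the DSMB plan:

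- State the time window to which each registry-based expected count refers.
- Define number of participants, and state when time at risk starts in each group.
- Re-index the rejection and graft-loss tables by accrued participant-time at risk in each group. Expected events are the registry rate per participant-month times accrued participant-months. Report events per participant-month.
- If the expected counts are for a short window, count only events and exposure inside that window.
- Keep the sponsor's own greater-than-50%, three-fold criterion and the three-event minimum. Recompute both tables from the stated expected counts, naming the probability model used.

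The cost is protocol and DSMB-plan wording, two recalculated tables, and more false pauses: about 1-12% per group of 200 for rejection under the criterion simulated here, against under 1% for the present table. Each false pause costs a DSMB review, and applying the rule to three groups and two event types adds to the total. The exact rate depends on the model the sponsor chooses. Re-indexing the mortality table is optional.

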12.7.2.2 Ad hoc DSMB Reviews

In addition to the pre-scheduled data reviews and planned safety monitoring, the DSMB may be called upon for *ad hoc* reviews. The DSMB will review any event that potentially impacts safety at the request of the protocol chair or DAIT/NIAID. In addition, the following events will trigger an *ad hoc* comprehensive DSMB Safety Review:

Any death that occurs in the study which is possibly or definitely related to study treatment regimen.

A Pausing Rule (outlined in Section 11.2) is met.

After review of the data, the DSMB will make recommendations regarding study conduct and/or continuation.

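### Over the planned 400 patients, the expected counts in Section 11.5 do not yield its pausing triggers, so at the larger group sizes a trigger does not mean what the text says; and rule 5 cannot act on excess deaths judged unrelated

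*Combined protocol and SAP*

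**What the plan says.** Section 11.5 (Study Pausing Rules) gives three count-based rules, each with a benchmark from registry data:

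- Rule 3, rejection: "approximately 5-6 rejection events would be expected over the course of the study".
- Rule 4, graft loss: "it is expected that there will be approximately 6-7 graft losses over the course of the study".
- Rule 5, mortality: "it is expected that there will be approximately 5 deaths over the course of the study".

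All three state the same criterion: "the study would be paused if there is a >50% chance that the observed event rate exceeds three times the expected rate". Each has a table of triggers at 13 sample sizes from 10 to 400, and rules 3 and 4 share one set of numbers. Rules 3 and 4 apply by group (vaccine alone, MMF withdrawal, CNI reduction). For rule 5, "The pausing rule will be applied to the study overall and by group". Rule 5 also requires that the excess "AND is determined to be possibly, probably or definitely related to a study intervention".

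Rule 1 pauses on "Any Grade 4 or 5 event that is definitely or possibly attributed to the study dose of vaccine or to immunosuppression reduction". Section 12.7.2.2 sends to ad hoc DSMB review "Any death that occurs in the study which is possibly or definitely related to study treatment regimen".

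Section 13.7 plans 400 patients, 200 per arm. Section 11.5 gives no per-participant rate, counting window, denominator or prior.

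**The concern.** A DSMB member will read a crossed trigger as meaning that the event rate has more likely than not tripled. If the expected counts refer to the 400 planned patients, three times expected is 15-18 rejections, 18-21 graft losses and 15 deaths at n=400. The tables print 11, 11 and 10. The stated meaning and the printed numbers cannot both hold on that reading, and the section does not give what is needed to tell which is at fault.

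The mortality rule raises a second question. Its benchmark of 5 deaths is described as independent of the interventions, yet it counts only deaths attributed to them. One such death already pauses the study under rule 1.

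**Working it through.** **Inputs.** N = 400 (Section 13.7). Expected count E: 5-6 rejections, 6-7 graft losses, 5 deaths (Section 11.5). Assumption: p0 = E/400, which gives 1.25-1.50%, 1.50-1.75% and 1.25%.

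Printed triggers at n = 10, 20, 30, 40, 50, 75, 100, 150, 200, 250, 300, 350, 400:

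- Rejection and graft loss: 3, 3, 3, 4, 4, 4, 5, 6, 7, 8, 9, 10, 11
- Death: 3, 3, 3, 4, 4, 4, 5, 5, 6, 7, 8, 9, 10

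**Rule as stated.** The trigger is the smallest x with P(p > 3·p0 | x events in n) > 0.5, where p has posterior Beta(a + x, b + n − x).

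**Attempt to reproduce the tables.**

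- Flat prior, E = 5: 0, 1, 1, 1, 2, 3, 4, 6, 7, 9, 11, 13, 15. This matches 2 rows for rejection and none for death.
- Beta(1, 1/p0 − 1), which has mean p0, E = 5: 3, 4, 4, 4, 5, 6, 7, 8, 10, 12, 14, 16, 18. This matches 2 rows in each table.
- A grid of Beta priors (a 0.05-8, b 0.05-400): at most 5 of 13 rows at any stated count.

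**Why a different fixed prior does not help.** From the approximate median of a Beta distribution, x ≈ 3p0·(n + a + b − 2/3) − a + 1/3. The prior shifts the intercept only, and the slope is 3p0. From n=50 to n=200:

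- Needed at E = 5, 6, 7: 150 × 0.0375 = 5.6; 150 × 0.045 = 6.75; 150 × 0.0525 = 7.9 events
- Printed: 7 − 4 = 3 (rejection, graft loss); 6 − 4 = 2 (death)

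**Chance of exceeding three times expected at the printed trigger.** Groups cannot exceed about 200, so for rules 3 and 4 only rows to n=200 are reachable. Rule 5 also runs overall, so its rows to n=400 are reachable.

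| Row | E | Flat prior | Beta(1, 1/p0 − 1) |
|---|---|---|---|
| 10 deaths in 400 | 5 | 11% | 3% |
| 6 deaths in 200 | 5 | 37% | 10% |
| 7 graft losses in 200 | 6 / 6.5 / 7 | 31 / 23 / 17% | 9 / 6 / 4% |
| 6 graft losses in 150 | 6 / 6.5 / 7 | 48 / 39 / 32% | 14 / 11 / 8% |
| 7 rejections in 200 | 5 / 5.5 / 6 | 52 / 41 / 31% | 18 / 12.5 / 9% |
| 5 rejections or graft losses in 100 | 5 / 6 / 7 | 82 / 70 / 56% | 33 / 24 / 17% |

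Under the flat prior every row to n=100 exceeds 50% at all stated counts, and the printed triggers there are mostly higher than the rule gives (3 against 0-1 at n=10-30). Under Beta(1, 1/p0 − 1) the printed triggers are equal to or lower than the rule gives in every row.

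**What does fit.** With Beta(1, 1/p0 − 1), multiplying all three expected counts by one factor between 0.46 and 0.475 reproduces all 39 rows at 6 rejections, 6 graft losses and 5 deaths. This corresponds to:

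- Rejection and graft loss: 6 × 0.46/400 = 0.69% to 6 × 0.475/400 = 0.71%
- Death: 5 × 0.46/400 = 0.575% to 5 × 0.475/400 = 0.594%
- Equivalent denominator: 400/0.475 = 842 to 400/0.46 = 870

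**Rule 5 beside rule 1.** The smallest rule 5 trigger is 3 deaths, all related. Grade 5 is death (Section 12.3.1), so one death possibly or definitely attributed to the vaccine or to immunosuppression reduction pauses under rule 1. Rule 5 could come first only for deaths due solely to a study procedure, if those count as a study intervention. Deaths judged unrelated count towards neither rule.

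**Rule 5 if made all-cause.** Using the printed overall triggers, a look at each tabulated n to 400 and an exact binomial recursion at p = 1.25%, 2.5% and 3.75%, the chance of a pause is 9%, 66% and 96%.

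**The case against.** The strongest reply is that 400 is a reading, not a stated denominator. The counts cover the study, while the safety windows differ: 60 days for the endpoints (Section 3.3.1), 6 months for SAEs (Section 12.4.1) and 12 months of follow-up (Section 11.1). The synopsis gives 13 months for screening, vaccination and follow-up, and 6/13 = 0.4615 lies inside the fitting range: it reproduces all 39 rows at 6, 6 and 5. Counts, criterion and tables could therefore be consistent, with only the window and prior undisclosed. This stands as a possible cause. It does not show that the text is right: Section 11.5 states neither window nor prior, and the same ratio matches only 11 of 13 rows at 5.5 rejections and 9 of 13 at 6.5 graft losses.

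It is also fair that the failure is not general. With 5 rejections expected and a flat prior, every reachable rejection row exceeds 50%, and rows 150 and 200 match exactly.

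On rule 5, the overlap makes the plan more protective, and the rule can still act after a rule 1 pause is lifted. Deaths judged unrelated still reach the medical monitor's monthly reports and the planned and discretionary DSMB reviews (Sections 12.7.1 and 12.7.2.1).

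A reader might infer that the triggers are too lax or too strict. The documents do not support either: the direction depends on n and on a prior that is not given. Nor is the shared rejection and graft-loss table evidence of a copying error, since both ranges include 6.

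**Conclusion.** The point holds as a minor one. On the assumption that the expected counts refer to 400 patients, no prior tried yields the printed tables. The clear failures among reachable rows are overall deaths at n=200-400, graft loss at n=150-200, and rejection at n=200 unless exactly 5 are expected under a flat prior. Confidence is high on that non-reproduction and on the overlap of rules 1 and 5. That one unstated rate, window or denominator explains it is an inference.

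It would go too far to say that the tables are wrong throughout, or that participants are less protected. The tables are coherent at lower rates, the pauses are temporary, and the primary analysis is unaffected.

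Rule 5 adds nothing to the first pause, apart from the procedure-only case. An excess of deaths judged unrelated has no count-based trigger.

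**What to change.** 1. For each outcome, state the expected proportion per participant, the counting window and the prior. Then correct either the expected counts or the description of what a trigger means, so that text and tables agree.
2. Leave the triggers unchanged unless the verified registry inputs require otherwise. Recomputing them from the stated counts could loosen them badly. At 5.5 rejections per 400, with a look at each tabulated n, the printed triggers pause by n=200 with probability 76% if the rate is tripled (4.5% at the expected rate). Triggers recomputed under Beta(1, 1/p0 − 1) would cut the 76% to 29%.
3. Remove the relatedness condition from rule 5, so that observed and expected deaths are counted on the same all-cause basis. The price is about a 9% chance of one temporary pause if deaths occur at 5 per 400. By-group looks would add some.

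The cost is a few hours of statistical work, a protocol text amendment and notification of the DSMB. No extra data or patients are needed.
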